## **OUTCOME MEASURES:**

Due to MOBILITY being a pragmatic and largely observational study, any participant who is deemed eligible by the above criteria will be enrolled in MOBILITY. These criteria, along with providing appropriate informed consent/assent, are the necessary criteria for participation in MOBILITY. We will continue to collect data in a naturalistic manner from all patients who have met these criteria regardless of whether they begin the intervention to which they have been randomized or have not attended all of their clinical follow up appointments. Patients will have follow-up study visits and data collected concurrent with their existing CLINICAL visit schedule.

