#### **Other outcome measures:**

Patient Health Questionnaire-9 (Item 9): Assesses current suicidality; 0 (not at all), 3 (nearly every day) scale.

Zucker Hillside Side Effects Form: Assesses intensity (1=not present, 4=severe) of adverse events in five domains (behavioral, neurological, cardiovascular, autonomic, GI side effects). Open ended AE (adverse event) questions at every visit.

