Participants randomized to treatment with MET will start at a recommended dose of 500 mg orally at night and slowly titrated in 2-week intervals to ensure that each patient achieves maximum insulin-sensitizing effects of the drug while minimizing the chance of side effects (see Table 1). We selected 50kg as the weight at which we felt comfortable increasing to a maximum total daily dose of 2000mg (1000mg twice daily). These youth will be at a low-end adult-comparable weight. We anticipate that most participants  $\geq$ 10 years old will be  $>50$ kg, which is the 95%ile for weight for 10-year-olds of both sexes. Children  $<50$ kg, likely those patients  $<10$  years, will have a reduced maximum daily dose of 1500mg. If

patients exhibit untoward gastrointestinal side effects while taking MET, clinicians will have the option to switch to an equivalent dose of the once-daily extended-release form of MET, which may alleviate side effects. If a patient does not tolerate a specific dose, the clinician will also have the option of reducing that dose by 500mg/day to a minimum recommended daily dose of 500mg twice daily. At Week 8, the dose for the <50kg group may be titrated to the maximum of 2000mg/day (1000mg twice daily) if tolerated and strategy, in general, MET will be at steady-state target levels well before key outcomes are assessed at Month 6. We will also recommend that MET be taken with food to minimize side effects. If a participant's BMI percentile <5% (=underweight) his/her treatment with MET will be discontinued. Although the risk of low vitamin B12 while taking MET is associated with age > 50 years and having type II diabetes, we will monitor B12 levels and a CBC throughout study participation.

Clinicians and patients must be willing to be randomized to either treatment arm. However, the clinician may choose to initiate or continue (for those on a subtherapeutic dose) metformin at their clinical discretion regardless of randomization following a recommended initial 3 month period of treatment. These patients' data will be considered in a different analytic group regardless of randomization.

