The basic model for outcomes will be a GLMM with change from baseline to either 6- or 24- months as the dependent variable. Independent variables will include fixed-effect terms for randomized treatment group (MET), baseline value of the outcome, and random site effects. For HTE analyses, a baseline value-by-MET interaction (to assess HTE due to baseline status) will be included, and for particular domains additional continuous or categorical covariates and treatment-by-covariate interaction terms will be added to assess HTE. Outcomes within each domain will share the same set of HTE terms, specified in the Specific Aims. Because the subgroups are in general correlated (e.g., duration of SGA treatment, weight gain history and psychotropic weight burden will be correlated with baseline BMI), we will include multiple first-order HTE terms simultaneously (to assess heterogeneity independently attributable to each moderator), but will also fit separate models for each term to gauge the impact of this correlation on our conclusions. Higher-order treatment-by-covariate interactions will not be included a priori, but will be explored with rigorous adjustment for multiple testing, using step-down testing (removing highest-order interaction terms first) or information criteria based on penalized likelihoods to guide model selection.

**Marginal Structural Modeling for Causal Inference:** SA1 concerns the overall and sub-group specific effects of MET on abrogation of weight gain (with changes in BMI z-score from baseline as outcomes) and metabolic health, particularly metabolic syndrome and its component criteria. BMI and adherence measures are obtained at all study visits, so our models for these measures will use all available observations by treating the longitudinal series of changes in these variables and SGA treatment as dynamically dependent on each other. We will use marginal structural models to address this bi-directional dependence, computing the probability of SGA treatment regimen change at each visit within weight gain treatment regimen groups and using appropriately normalized versions of the inverse of the probability as the stabilized weights.

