**Other potential risks:** To guard against frustration and fatigue, questions and surveys have been carefully chosen by patients, parents, and stakeholders. However, when necessary, assessments can be divided to decrease the frustration and fatigue. In addition, research staff will be hired based on their research experience and work with children and adolescents. Lastly, patients and their parent(s)/legal guardian(s) will be advised that they do not have to participate in the study and that their participation is voluntary and refusal to participate will not impact their clinical care in any way. Their alternative to study participation is to continue to receive standard clinical care. **Additional weight gain or metabolic abnormalities:** Patients in the study will be closely monitored for weight gain and metabolic abnormalities. Clinicians, parents, or patients can discontinue assigned study treatment at any point, but will still be monitored for up to 24 month. If a patient continues to have substantial weight gain ( $> 10\%$ ) in the LIFE group, a clinician might decide to add MET to the treatment if clinically indicated. Likewise, if the patient is randomized to the MET + LIFE group and continues to have substantial weight ( $> 10\%$ ) they will have the option to continue MET and/or add another treatment or switch the patient's treatment for BSD, whichever is clinically indicated. If a participant's BMI percentile 5% (= underweight) his/her treatment with MET will be discontinued.

Although the risk of low vitamin B12 while taking MET is associated with age  $> 50$  years and having type II diabetes, we will encourage clinicians to monitor B12 levels and a CBC throughout study participation. We will educate all study-related clinicians about this potential side effect of metformin and the very rare clinical manifestations of MET-related vitamin B12 deficiency (i.e., peripheral neuropathy and pernicious anemia).

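### No safety summary by actual metformin exposure is planned, and the only stated model that could cover side effects compares randomised arms, which would understate metformin's harms

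*Combined protocol and SAP*

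**What the plan says.** Under Other outcome measures, the side-effect form is described thus: "Assesses intensity (1=not present, 4=severe) of adverse events in five domains". Table 2 schedules it at baseline, month 6 and month 24 only. Open-ended adverse-event questions are asked at every visit, and the medication list is also collected at every visit.

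Section E.b (Analyses of Specific Aims) gives the general model: "The basic model for outcomes will be a GLMM with change from baseline to either 6- or 24- months as the dependent variable". Its treatment term is the arm as randomised: "Independent variables will include fixed-effect terms for randomized treatment group (MET), baseline value of the outcome, and random site effects". A second approach, marginal structural modelling, covers BMI and adherence. Its weights come from "computing the probability of SGA treatment regimen change at each visit within weight gain treatment regimen groups", so they concern antipsychotic changes and not starting or stopping metformin.

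Three provisions let arm and exposure part company:
- Outcome Measures: patients are followed "regardless of whether they begin the intervention to which they have been randomized".
- Section G.a (Other potential risks): "Clinicians, parents, or patients can discontinue assigned study treatment at any point, but will still be monitored for up to 24 month". The same paragraph lets a clinician add metformin for a LIFE patient with continuing weight gain.
- The treatment text after Table 2: "the clinician may choose to initiate or continue (for those on a subtherapeutic dose) metformin at their clinical discretion regardless of randomization". The plan recommends that this wait until the first three months are over. The next sentence assigns these patients to a separate analysis group whatever their randomised arm. Section E.b does not mention or define that group.

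The safety monitoring text provides for DSMB review of adverse events twice a year. It gives no safety population, exposure definition or on-treatment summary.

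**The concern.** For efficacy, comparing arms as randomised answers the pragmatic question. For harm, the same comparison is not conservative. If a side effect follows the drug, each MET patient off metformin and each LIFE patient on it brings the two arms closer together. A MET patient who stops because of diarrhoea and recovers before month 6 has a clean form at month 6.

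The trial could then report similar side effects in both arms for a drug whose gastrointestinal effects section G.a lists as common, in a paediatric use that the same section says is not FDA-approved. Readers might take that as evidence of tolerability when it partly reflects mixed exposure.

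**Working it through.** The plan states no figure on this point, so there is none to reproduce. The available text gives no rates of non-start, stopping or off-assignment metformin, and no side-effect rates by arm. What follows is an illustration under assumed rates.

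**Inputs**
- From the plan: 1,800 patients randomised 1:1, so 900 per arm.
- Assumed: true risk of a side effect 5% off metformin and 10% on it, a true difference of 5 points. The plan says only that the common effects occur in at least 5%.
- Assumed: s = share of MET patients off metformin at assessment and c = share of LIFE patients on it. The (s, c) pairs are (10%, 5%), (24%, 15%) and (40%, 30%). The 24% is borrowed from the metformin-arm dropout in the earlier trial described under Preliminary Studies. That is study dropout, not stopping the drug while in follow-up, so it serves only as a mid-range value.
- Assumed: two-sided 5% test of two proportions, normal approximation.

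**Reading 1: LIFE patients who take metformin stay in the LIFE arm**

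MET risk = 10% − s × 5 points; LIFE risk = 5% + c × 5 points; fraction kept = 1 − s − c.

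| s, c | MET | LIFE | Difference (points) | Fraction kept | Power, 900 per arm |
|---|---|---|---|---|---|
| 0, 0 | 10.0% | 5.0% | 5.0 | 100% | 98% |
| 10%, 5% | 9.5% | 5.25% | 4.25 | 85% | 93% |
| 24%, 15% | 8.8% | 5.75% | 3.05 | 61% | 70% |
| 40%, 30% | 8.0% | 6.5% | 1.5 | 30% | 23% |

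At the roughly 90% retention the plan expects (about 810 per arm), the first and last powers become 97% and 21%.

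**Reading 2: LIFE patients who take metformin go to the separate group and leave the comparison**

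The LIFE patients who remain are all off metformin, so LIFE risk stays at 5%. The fraction kept is 1 − s, and LIFE size is 900 × (1 − c).

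| s, c | MET | LIFE | LIFE n | Difference (points) | Fraction kept | Power |
|---|---|---|---|---|---|---|
| 10%, 5% | 9.5% | 5.0% | 855 | 4.5 | 90% | about 95% |
| 24%, 15% | 8.8% | 5.0% | 765 | 3.8 | 76% | 86–87% |
| 40%, 30% | 8.0% | 5.0% | 630 | 3.0 | 60% | 64–67% |

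The power ranges reflect pooled versus unpooled variance. Both readings shrink the difference. Reading 2 shrinks it less, but it takes metformin-exposed patients out of the arm comparison without saying where their events are reported.

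**Direction.** Both formulas assume that stopping is unrelated to having the side effect. If patients stop because of it, those still on metformin at month 6 are the ones who tolerated it, and the difference shrinks further than shown.

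**The case against.** **The model may not be meant for side effects.** It sits under the specific aims, and no aim mentions side effects. A reader might infer that the plan commits to analysing harms with it. The text does not say so; the model reaches them only through the general word for outcomes. This stands. If the model does not apply, however, no side-effect analysis is stated at all, and the remedy is the same.

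**It is not the only outcome model.** Marginal structural models are also stated. True, but they cover BMI and adherence and weight on antipsychotic changes.

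**LIFE patients on metformin need not count as controls.** A reader might infer that their events are scored against LIFE. The separate-group sentence says otherwise, so the most severe figures above (30% kept, 23% power) require that sentence to be set aside. This stands, and it is why both readings are shown. The sentence does not deal with MET patients who never start or who stop.

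**Harms are not unobserved.** Adverse events are asked about at every visit and go to the DSMB, so an early event in a patient who later stops can be recorded. Titration runs over weeks 1–8 and off-assignment metformin is recommended only after 3 months, so LIFE crossover should affect early gastrointestinal effects little. The background also reports minimal discontinuation in the team's own placebo-controlled metformin study. All of this limits the likely size. But DSMB monitoring is not a reported analysis, and non-start and early stopping still apply.

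**The power figures are rough.** They treat a yes/no event, whereas the form is a 1–4 intensity score. Agreed; they show the order of the effect and do not predict it.

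**Conclusion.** The gap is real and should be closed. The available text specifies no side-effect analysis by metformin exposure, and the one model that could apply compares arms that the design allows to drift from exposure. If used for harms, it would bias the difference towards zero. Under the assumed rates, the arm comparison keeps 30% to 85% of the true difference if LIFE crossovers stay in their arm, and 60% to 90% if they are removed. The direction requires only that risk follows exposure. The size rests wholly on assumed rates.

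The separate-group sentence and the randomised-group term in section E.b conflict and must be reconciled for safety reporting.

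Two stronger conclusions do not follow. The documents do not show that harms will in fact be diluted by any particular amount. Nor does the plan's description of risk as minimal depend on this comparison; it is a justification made before the trial. The primary BMI z-score analysis is not affected by this point.

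**What to change.** Add to section E.b, alongside the randomised comparison:

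- Descriptive tables of adverse events from every visit, classified by metformin exposure at event onset and taken from the per-visit medication list. Show time before starting, on, and after stopping metformin separately. Count LIFE patients' time on metformin as exposed.
- Side-effect form scores and available safety laboratory results (B12, creatinine, ALT) by exposure at assessment. Add the caveat that a patient who stopped because of a side effect and recovered will not show it on the month 6 or month 24 form. For such patients only the visit-level adverse events help.
- A statement that the separate-group sentence in the treatment text removes no patient from the safety tables, and a definition of that group that agrees with the randomised-group term.

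The cost is SAP wording and one extra set of tables. The medication list and adverse-event questions are already scheduled at every visit, and no visit, dose or clinical rule changes. The available text does not say that an onset date is recorded for each event. If it is not, the interval between visits would have to serve. The main drawback is that a comparison by exposure is not randomised: patients who stay on metformin differ from those who stop. The tables should be labelled descriptive and read beside the randomised comparison.

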**H2.3:** The overall effects of MET treatment on SGA adherence will be mediated by degree of weight abrogation, and this relationship will be stronger among girls than boys. We anticipate a possibly complex relationship between abrogation of weight gain (associated with MET) and SGA adherence, because weight gain may also be avoided via SGA non-adherence (at the probable cost of sub-optimal psychiatric outcomes; see Specific Aim 3). A statistical framework (marginal structural models) to accommodate this possibility is described in the Statistical Analysis Plan.

**Specific Aim 3:** Assess the overall and subgroup-specific impact of MET+LIFE vs. LIFE alone on **psychiatric symptom burden, psychotropic treatment changes, and overall and weight-related QoL**, including assessment of how these effects are mediated by MET effects on weight gain and SGA adherence.

**H3.1:** Overall, assignment to treatment with MET will be associated with lower psychiatric symptom burden, decreased risk for symptom-driven treatment changes, and greater improvements in overall and weight-related QoL than LIFE alone at both 6 and 24 months, post-randomization.

**H3.2:** (HTE): MET effects on psychiatric symptoms will be smaller in patients who meet full DSM criteria for a BSD.

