for data entry and real time validation (e.g., automated data type and range checks); 2) HIPAA-compliant and 21 CFR Part 11-ready audit trails for tracking data manipulation and exports; 3) record locking and electronic signature functions; 4) control of view/edit rights; 5) a tool for reporting, monitoring and querying patient records; and 6) automated export to common statistical packages. REDCap is hosted on a network specially designed to support the rigorous security and compliance requirements of clinical research projects. Administered by the CCHMC Division of Biomedical Informatics, this network features multiple firewalls and a central facility for managing hosted systems and users, creating another layer of access control and audit capability on top of what REDCap already provides (e.g., user access can be monitored and controlled at the network level without making any changes within REDCap itself). These capabilities are available to authorized network administrators and REDCap study owners only, and user access changes are documented by an audit trail. The data management team will monitor the database throughout the study to assure that data are complete and accurate.

**Analyses of Specific Aims:** Each specific aim involves assessment of domains that are hypothesized to be affected by MET either directly or indirectly through other domains. Our approach to potential HTE distinguishes effect moderators from mediators of distal outcomes. Moderators include fixed patient characteristics and pre-treatment covariates values. Mediators include variables that are hypothesized to be affected by MET treatment and that may in turn affect other outcomes. We will utilize generalized linear mixed models (GLMM), which allow for outcomes from a range of distributions and will include random effects to account for unspecified causes of variation among sites and patients, and subgroup-specific coefficients to assess HTE.

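### The marginal structural model weights only for SGA regimen change, which leaves the H2.3 mediator, weight change, confounded by adherence history

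*Combined protocol and SAP*

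**What the plan says.** H2.3 in Section A reads: "The overall effects of MET treatment on SGA adherence will be mediated by degree of weight abrogation". The same paragraph admits that "weight gain may also be avoided via SGA non-adherence", and answers: "A statistical framework (marginal structural models) to accommodate this possibility is described in the Statistical Analysis Plan". Specific Aim 3 adds a second mediation question, "including assessment of how these effects are mediated by MET effects on weight gain and SGA adherence".

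The statistical text is in Section E.b. Under Analyses of Specific Aims: "Mediators include variables that are hypothesized to be affected by MET treatment and that may in turn affect other outcomes". No mediator model or indirect-effect estimand follows. The basic model takes change from baseline as the outcome, with randomised arm, the baseline value of the outcome and random site effects. The paragraph on marginal structural modelling opens on Aim 1. It says that BMI, adherence and SGA treatment depend on one another over time, and builds stabilised inverse-probability weights by "computing the probability of SGA treatment regimen change at each visit within weight gain treatment regimen groups". No other probability is modelled, and the covariates for this one are not listed.

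Adherence is a separate measure: missed and partial doses in the past week (Section E.a), expressed as treatments taken over treatments prescribed (Section E.b).

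**The concern.** Inverse-probability weighting removes confounding of the variable whose probability is modelled. Here that is SGA prescribing. In H2.3 the exposure of interest is weight change and the outcome is adherence. Past adherence raises weight and also predicts later adherence, so it confounds exactly the association that H2.3 needs. A patient who skips doses of an unchanged prescription contributes no regimen change, so the weights cannot act on that path.

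At stake is the mediation part of Aims 2 and 3. Adherent patients gain more weight. An analysis that ignores this can suggest that preventing weight gain goes with worse adherence when there is no such effect, or when the effect runs the other way.

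**Working it through.** **1. Is there a figure to reproduce?** No. The documents give no effect size, SD or power for the mediation analysis. The size has to be shown under stated assumptions.

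**2. Null case in closed form.** Suppose weight has no effect on adherence and no prescription changes, so all planned weights equal 1. This isolates the missed-dose path; step 4 relaxes it.

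From the documents: metformin effect on BMI z of -0.088 - 0.040 = -0.128 (IMPACT, 24 weeks, Section C). N = 1600, close to 1800 × 0.9 = 1620 (about 90% retention, Section F.f).

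Assumed: six intervals; adherence A with SD 1 and visit-to-visit correlation r = 0.8; BMI z change per interval = arm effect + g × previous adherence + noise with SD 0.12.

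The correlation of baseline adherence with total gain is g × (1 + r + … + r^5) / SD(gain). At g = 0.01 this is 0.01 × 3.689 / √(0.0864 + 0.0024 + 0.0041) = 0.0369 / 0.305 = 0.12. The three variance terms are noise (6 × 0.12²), adherence (g² × 24.49) and arm (0.128² / 4).

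Regress final adherence on total BMI z change, arm and baseline adherence:

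- b = gS / (6 × 0.12² + g²V)
- S = Σ r^(6-s)(1 - r^(2s)) over s = 1 to 5 = 1.984
- V = variance of A1 + … + A5 given A0 = 10.87
- SE = √[(1 - r^12 - b·gS) / (N(6 × 0.12² + g²V))]

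At g = 0.01: b = 0.01984 / 0.08749 = +0.23; SE = 0.081; z = 2.79; chance of p < 0.05 = 80%.

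| g | correlation | b (truth 0) | SE | significant, formula | significant, simulation |
|---|---|---|---|---|---|
| 0.005 | 0.06 | +0.11 | 0.082 | 29% | 28% |
| 0.01 | 0.12 | +0.23 | 0.081 | 80% | 83% |
| 0.02 | 0.23 | +0.44 | 0.079 | 100% | 100% |

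The apparent indirect effect of metformin is -0.128 × b, that is -0.015, -0.029 and -0.056 SD of adherence, where the truth is zero. Conditioning on prior adherence brings the simulated false-positive rate to 5-8%.

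With BMI z change at mid-follow-up instead (three intervals; S = 0.360, V = 1.526), b is +0.04, +0.08 and +0.16. The formula gives 6.5%, 11% and 30% significant; simulation gave about 8% to 34%. An earlier mediator reduces the bias without removing it.

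**3. True effect present.** Let a BMI z gain lower adherence by 0.30 SD per unit in the same interval. At the same three correlations the baseline-adjusted estimates were -0.07, +0.04 and +0.26. Conditioning on adherence history gave about -0.30.

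**4. With prescription changes and the planned weights.** Simulation of 60,000 patients per scenario over six visits. Regimen change depended on prior BMI z and adherence. Stabilised weights for regimen change were applied, and baseline adherence and cumulative regimen changes were adjusted. Assumed ranges: g = 0, 0.01, 0.02, 0.04; true weight-to-adherence effect -0.2, -0.5, -1.0; r = 0.3, 0.8. The coefficients accumulate over visits, so compare signs with the truth, not sizes.

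- No adherence-to-weight path (g = 0): right sign in 6 of 6 scenarios.
- Path present (g > 0): wrong sign in 8 of 18 using previous-visit weight change and in 16 of 18 using same-visit change.
- Example (g = 0.02, truth -0.50, r = 0.8): unweighted +0.74, weighted +0.72 (previous visit); weighted +1.30 (same visit). The metformin effect on BMI z was -0.096, so the one-visit indirect effect moves from -0.096 × -0.50 = +0.048 to -0.096 × 0.72 = -0.069 SD.
- Conditioning on prior adherence: right sign in 24 of 24 (-0.51 in the example).
- Weights for BMI z change itself: right sign in 23 of 24. In the exception the effective sample fell to 25%.

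**The case against.** The best defence is that the plan is loose here rather than wrong. Its wording about mutual dependence over all visits could be read to include lagged history, and a model with lagged adherence works. That stands against saying that the plan cannot estimate the mediation, which a reader might infer. The outcome model is not fully specified, so the documents support only this: the weights as stated do not do the job assigned to them, and no other step is written down that does.

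The planned baseline adjustment also helps. It shrinks the bias, and the figures above include it, but it does not remove it.

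Regimen change is undefined, and the medication list is taken at every scheduled visit, so recorded stopping of an SGA might count. That narrows the gap to missed doses on an unchanged prescription. Weight change, the H2.3 mediator, would still have no model.

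A reader might infer that the sign will be reversed. It was right in 10 of the 18 previous-visit scenarios, and the strength and persistence of the adherence-to-weight path are not in the documents. Reversal is possible, not predicted.

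A reader might also object that separate natural indirect effects are not identified in Aim 3. The plan never claims them; it promises only an assessment of mediation.

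**Conclusion.** The concern holds as a mismatch between stated purpose and stated method. Marginal structural models are offered for the feedback from non-adherence to weight, but the weights address SGA prescribing. As written, the weight-to-adherence estimate is biased towards more weight gain going with better adherence. In the null case this gives about 28% to 100% false positives with total weight change and about 8% to 34% with mid-follow-up change. These figures rest on assumed correlations (0.06 to 0.23 with BMI z gain; 0.8 between visits), on the assumed BMI z noise, and on adherence measured without error.

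The problem should be fixed, but it is confined to the mediation hypotheses. A reader might take it as a threat to the trial's main result. It is not: H1.1, H2.1 and H3.1 compare randomised arms, and this issue does not bias them.

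**What to change.** For H2.3, state the time order: BMI z change up to the previous visit, then SGA adherence at the next. Condition the mediator-outcome model on prior SGA adherence, SGA regimen, prior BMI z, YMRS, CGI-S and PROMIS Depression, and include the sex comparison that H2.3 calls for. Name the indirect effect to be reported, and define SGA regimen change.

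Weights for BMI z change can serve as a sensitivity analysis, with truncation and effective-sample diagnostics set in advance because such weights can be unstable.

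For Aim 3, report the joint indirect effect through weight and adherence together. State how regimen-change weights are used there, since H3.1 also has "decreased risk for symptom-driven treatment changes" as an outcome.

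The cost is SAP wording, more analysis work and some precision. Table 2 already schedules every variable at every visit, so no new data are needed. Section E.a expects missed visits, so the SAP must say how incomplete histories are handled, for example by multiple imputation. Conditioning works only as well as adherence is measured, so the imputed electronic-monitoring values and the self-report should both be run. Settle all this before outcome data are analysed.
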